6.2 Description of Evaluations

6.2.1 Screening Evaluation

These evaluations occur to determine if the candidate is eligible for the study.

Definitions of the column headings in the Schedule of Evaluations (Section 6.1): (1) Assessment refers to the specific assessments as listed in the first column that will be performed at each of the study visits; (2) Visit 1 (Day 0) refers to all of the assessments that will occur at the first study visit; (3) Visits 2 to 13 refer to the assessments that will occur at each of the study visits 2 through 13 which correspond to the TARA study intervention sessions 1 through 12 (i.e., Study Visit 2 is TARA study intervention session 1 since the first TARA study intervention session will take place on Study Visit 2); (4) Final Visit 14 refers to all of the assessments that will occur on the final study visit which will be Visit 14. Please note that in the above Schedule of Evaluations (Section 6.1), the AE and SAE forms only will be completed if an AE and/or SAE are reported by a participant. In addition, if a participant prematurely leaves the study, all of the assessments listed under the final study visit 14 column will be performed.

A phone pre-screening evaluation will occur to determine if the candidate adolescent is eligible for the study prior to the initial visit, and a screening evaluation will occur at Visit 1 (Day 0) to determine if the candidate is eligible to enter the study.

Consenting Procedure

A trained research staff member who will have at least a college degree (i.e., Bachelor's degree or higher) will perform the following informed consent process.

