6.2.4 Followup Visits

The following study visits must be performed on the weeks indicated above in the Schedule of Evaluations (please see Section 6.1) plus/minus 5 (five) *working* days (i.e., Monday through Friday, not including weekends and holidays):

- Visit 1:
 - Informed Consent Form
 - Medical History Form
 - Inclusion/Exclusion criteria form
 - Enrollment/Randomization form
 - MRI Screening Form & urine pregnancy test
 - MRI brain scan
 - Demographics assessment (electronically in Qualtrics)
 - SDQ assessment (electronically in Qualtrics)
 - Baseline Checklist
- Visit 2 through Visit 13:
 - Child Session Rating Scale (CSRS)
 - Child Outcome Rating Scale (CORS) including the question: "Has there been any significant unfavorable change in your mental or physical health since last class?" (please see Appendix. Not a source document.)
 - Adverse Events (if answered Yes the question above in CORS)
 - Serious Adverse Events (if answered Yes to the SAE question in the Adverse Event form)
 - On Study Visit Checklist Form (modified to include Treatment Administration information)

6.2.5 Completion/Final Evaluation.

The following assessments will be performed at the participant's final visit (Visit 14):

- SDQ assessment (electronically in Qualtrics)
- MRI Screening Form & urine pregnancy test
- MRI brain scan
- Child Outcome Rating Scale (CORS) including the question: "Has there been any significant unfavorable change in your mental or physical health since last class?" (please see Appendix. Not a source document.)
- Adverse Events (if answered Yes the question above in CORS)
- Serious Adverse Events (if answered Yes to the SAE question in the Adverse Event form)
- Study Completion form.

For study participants who discontinue the study intervention early, all of the following assessments will be performed:

- SDQ assessment (electronically in Qualtrics)
- MRI Screening Form & urine pregnancy test
- MRI brain scan
- Child Outcome Rating Scale (CORS) including the following question: "Has there been any significant unfavorable change in your mental or physical health since last class?" (please see Appendix. Not a source document.)
- Adverse Events (if answered Yes the questions above in CORS)
- Serious Adverse Events (if answered Yes to the SAE question in the Adverse Event form)
- Study Completion form.

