7.3 Adverse Events and Serious Adverse Events

In the present study, an adverse event and serious adverse event will be defined as follows:

An adverse event (AE) will be defined as any unfavorable and unintended diagnosis, symptom, sign (including an abnormal laboratory finding), syndrome or disease which either occurs during the study, having been absent at baseline, or if present at baseline, appears to worsen. Adverse events will be recorded regardless of their relationship to the study intervention.

A **serious adverse event (SAE)** will be defined as any untoward medical occurrence that results in death, is life threatening, requires inpatient hospitalization or prolongation of existing hospitalization, results in persistent or significant disability/incapacity, or is a congenital anomaly.

Since we do not anticipate any laboratory value changes due to the TARA study intervention, no laboratory values will be collected as part of the current protocol; thus, no laboratory values will be collected to assess safety.

Solicited adverse events will be captured in the following manner: (1) the Child Outcome Rating Scale (CORS) including the following question: "Has there been any significant unfavorable change in your mental or physical health since last class?" will be administered at every TARA session (please see Appendix. Not a source document.); (2) if the participant answers "no" to this question on the CORS, then no additional information will be requested; (3) if the participant answers "yes" to this question on the CORS and the reported event meets the definition of an adverse event given above, then the research assistant or another study staff member will ask the participant for additional details regarding the participant's answer to the CORS question and this information will be recorded in the Adverse Event form within 24 hours of the TARA study intervention session.

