In order to assure that the reporting and data collection systems avoid double capture of solicited and unsolicited events, we have implemented the following items in our protocol: (1) We will ask all of the participants to report any unsolicited events in the CORS after the question, "Has there been any significant unfavorable change in your mental or physical health since the last class?"; (2) If a participant reports an unsolicited event to any of the study staff, the study staff member will ask the participant to write down this information in the CORS in order to avoid double capture of the event; (3) We also will specifically instruct our research assistants and staff to not duplicate the recording (i.e., double capture) of the same solicited and unsolicited events; (4) At the weekly clinical trial research lab meetings, the PIs (Drs. [name] and [name]) will review with the research staff all of the CORS forms, AE and SAE forms for the prior week in order to ensure that there is no double capture(s) of any solicited and unsolicited event(s).

Time Period and Frequency for Event Assessment and Follow-Up

Unanticipated problems will be recorded in the data collection system throughout the study.

To satisfy the requirement for prompt reporting, unanticipated problems will be reported using the following timeline:

- Unanticipated problems that are serious adverse events will be reported to the IRB, Independent Safety Monitors, and NCCIH within 7 days of the investigator becoming aware of the event.
- Any other unanticipated problem will be reported to the IRB, Independent Safety Monitors, and NCCIH within 15 days of the investigator becoming aware of the problem.

All unanticipated problems will be reported to appropriate institutional officials (as required by an institution's written reporting procedures), the supporting agency head (or designee), and OHRP within one month of the IRB's receipt of the report of the problem from the investigator.

Adverse Event Reporting

SAEs that are unanticipated, serious, and possibly related to the study intervention will be reported to the Independent Safety Monitors, IRB, and NCCIH in accordance with requirements.

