7.4 Reporting Procedures

Please see below, Table A, for details of the reporting procedures and timelines, including the individual responsible for each step (e.g., the PIs, the Independent Monitors, etc.). The medical director, [name] (co-PI), will make the decision regarding determining the relatedness and severity of any and all AEs and SAEs. The appropriate AE and SAE forms will be completed. The completed AE and SAE forms will be sent and distributed to the appropriate individual or group of individuals (i.e.,

UCSF IRB, NCCIH) as stated below in Table A (please see below, Table A). The PIs will record all reportable events with start dates occurring any time after informed consent is obtained until 7 days (for non-serious AEs) or 30 days (for SAEs) after the last day of study participation. A research assistant will perform the duties of the Internal QA reviewer. At each study visit, the investigator will inquire about the occurrence of AE/SAEs since the last visit. Events will be *followed* for outcome information until resolution or stabilization.

Table A

Data type	Frequency of review	Reviewer
Subject accrual (including compliance with protocol	Monthly	PIs, Internal QA Reviewer
enrollment criteria)	Semi-annually	Independent Monitors
Status of all enrolled subjects, as	Monthly	PIs, Internal QA Reviewer
of date of reporting	Semi-annually	Independent Monitors
Data entry quality control checks on 100% of charts	Weekly	QA Reviewer
Adherence data regarding study	Monthly	PIs, Internal QA Reviewer
visits and intervention	Semi-annually	Independent Monitors
AEs and rates (including out-of-	Monthly	PIs, Internal QA Reviewer
range lab values)	Semi-annually	Independent Monitors
	Annually	NCCIH
SAEs (unexpected and related)	Per occurrence	PIs, Independent Monitors NIH/NCCIH
SAEs (expected or unrelated)	Per Occurrence	PIs, Internal QA Reviewer
	Annually	Independent Monitors, NIH/NCCIH
Unanticipated Problems	Monthly	PIs, Internal QA Reviewer
	Per Policy	IRB

Reporting Changes in Study Status

During the funding of this study, any action by an IRB, the Independent Monitors, or one of the study investigators that results in a temporary or permanent suspension of the study will be reported to the NCCIH Program Official within 3 business days of notification.

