While an enrolled participant is temporarily discontinued from the study intervention (e.g., cold), no additional evaluations will be performed until the participant resumes with participating in the study intervention. Once the participant resumes with participating in the study intervention, the evaluations as specified above (please see Section 6.1, Schedule of Evaluations) will then be performed based upon which session number the participant resumes her/his participation in the study.

If an enrolled participant is permanently discontinued from study intervention, then the participant will be followed for one additional visit in order to allow for all of the final visit (Visit 14) assessments to be performed. Once the final visit (Visit 14) assessments are completed, the participant will no longer continue to be followed except to follow any AEs or SAEs as stated above in Section 7.4 (i.e., until 7 days [for non-serious AEs] or 30 days [for SAEs] after the last day of study participation).

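### AE and SAE forms open only on a participant's report, which contradicts the Section 7 duty to record all events, so events known only from others may be missed

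*Combined protocol and SAP*

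**What the plan says.** **Form-level rule.** Section 6.2.1, in its notes on the Schedule of Evaluations, says that "the AE and SAE forms only will be completed if an AE and/or SAE are reported by a participant". For Visits 2 to 13, Section 6.2.4 lists the first form as "Adverse Events (if answered Yes the question above in CORS" and the second as "Serious Adverse Events (if answered Yes to the SAE question in the Adverse Event form". Section 6.2.5 repeats both triggers for Visit 14 and for early discontinuation, and Section 10.1 repeats them in the list of data forms. Under Section 7.3, a No on the CORS ends the inquiry. If a participant tells staff of an unsolicited event, "the study staff member will ask the participant to write down this information in the CORS".

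**Wider duty.** The opening of Section 7 has any AE that occurs assessed by the medical director and entered on the AE form. Section 7.2 has every AE collected on that form at the TARA visits, and the SAE form completed once an event is classified as serious. Section 7.4 says "The PIs will record all reportable events with start dates occurring any time after informed consent is obtained", up to 7 days (non-serious) or 30 days (serious) after last participation. Sections 7.4 and 7.5 have the investigator ask at each visit about events since the previous one.

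**Related text.** Section 7.3 defines an SAE as "any untoward medical occurrence that results in death, is life threatening, requires inpatient hospitalization or prolongation of existing hospitalization", among other criteria. Section 8 says that during a temporary discontinuation "no additional evaluations will be performed until the participant resumes with participating in the study intervention". Section 6.2.5 says that no specific follow-up requirements apply after the intervention is stopped, and gives AE monitoring and reporting as an example.

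**The concern.** The defining features of an SAE are those that most often prevent self-report. Section 6.2.5 itself names death, severe disability, severe accident and severe illness among its reasons for early termination. A form rule that depends on the participant speaking does not fit these events. Most participants are minors, so a parent will often be the first to tell the study.

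The safety conclusions rest on these forms. Sections 7.1 and 9.5.2 call the intervention safe if fewer than 15% of participants have a related grade 2 or 3 event. Section 9.4 triggers a safety review at 15%, and Section 9.6 compares grade 2 or higher events between arms. An event that opens no form enters none of these.

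**Working it through.** The plan states no figure on this point, so there is none to reproduce. The check is textual, followed by an illustration under assumed rates.

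**Step 1. Apply each rule to concrete cases.**

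| Event becomes known through | Form-level rule (6.2.1, 6.2.4, 6.2.5, 10.1) | Wider duty (7, 7.2, 7.4, 7.5) |
|---|---|---|
| Participant's Yes on the CORS | Form opened | Recorded |
| Participant tells the class leader or staff | Participant writes it in the CORS, then form | Recorded |
| Facilitator sees a reaction, participant answers No | No form | Recorded |
| Parent reports a hospitalization | No form | Recorded, SAE form on classification |
| Death, as foreseen in 6.2.5 | No form | Recorded, SAE form on classification |

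The rules agree on the first two rows and conflict on the last three.

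**Step 2. Does the wider duty supply the missing route?** Only in part. Section 7.2 ties collection to the TARA visits, and the inquiry in 7.4 and 7.5 takes place at study visits, so both need the participant to be present. Section 7.4 gives the PIs a duty without limit by source, but not the path by which a third-party report reaches them or a form. Section 10.1 has research assistants fill out the forms, and the instruction attached to the forms is the restrictive one.

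**Step 3. Participants who are away.** The Section 8 pause applies to temporary discontinuation, and evaluations resume on return. The investigator's question then looks back to the last visit. The CORS question looks back to the last class, which could mean the last class held or the last attended. Those who leave early or stop permanently are due the Visit 14 assessments, which include the CORS question. After that, 6.2.5 (no specific requirements) conflicts with the 7-day and 30-day window in 7.4, 7.5 and 8.

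**Step 4. Direction and possible size.** Let p be the true proportion of participants with a related grade 2 or 3 event, and c the proportion of those participants whose event is recorded. The recorded count is then X ~ Binomial(N, p × c). Neither p nor c is in the documents; both are assumptions. For the TARA arm, 15% × 50 = 7.5, so the threshold is reached at 8. For all enrolled, 15% × 100 = 15.

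| N, threshold | p | c = 1 | c = 0.9 | c = 0.75 | c = 0.5 |
|---|---|---|---|---|---|
| 50, at least 8 | 0.15 | 0.48 | 0.36 | 0.20 | 0.03 |
| 50, at least 8 | 0.20 | 0.81 | 0.70 | 0.48 | 0.12 |
| 50, at least 8 | 0.25 | 0.96 | 0.90 | 0.75 | 0.28 |
| 100, at least 15 | 0.15 | 0.54 | 0.37 | 0.15 | 0.01 |
| 100, at least 15 | 0.20 | 0.92 | 0.82 | 0.54 | 0.07 |
| 100, at least 15 | 0.25 | 0.995 | 0.98 | 0.86 | 0.27 |

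Each entry is the chance that the recorded count reaches the threshold. It falls as c falls, so under-recording always favours a finding of safety. The table shows sensitivity only and does not estimate the loss in this trial.

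**The case against.** The sentence in 6.2.1 is a note to a schedule that marks AE and SAE at every visit from 2 to 14. It may mean only that a form is not filled out routinely at each visit, rather than that other informants are excluded. Section 7 is the governing safety section and sets no limit by source. Participants can speak to the class leader or staff, and the PIs review the CORS, AE and SAE forms weekly. The AE and SAE forms and the data safety monitoring plan are not in the text available here and might contain a third-party route.

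Much of this stands, and it rules out stronger conclusions that a reader might draw:

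- That events known from others are simply not recorded. Sections 7, 7.2, 7.4 and 7.5 require the opposite.
- That the CORS is the only scheduled safety question. Sections 7.4 and 7.5 add the investigator's inquiry at each visit.
- That the share of sessions a participant may miss measures the loss. Missed sessions are not missed events, and the next inquiry looks back.
- That the 7-day and 15-day reports depend on a participant-triggered form. Section 7.3 starts those clocks when the investigator becomes aware.

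The objection does not remove the conflict. The note could be read as harmless if it stood alone, but Sections 6.2.4, 6.2.5 and 10.1 carry the same condition into the form triggers, and Section 7.3 sends even unsolicited events back through the participant's own entry.

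**Conclusion.** The point holds as an internal contradiction with a missing procedure. The form-level sections make the participant the trigger for the AE and SAE forms, while Section 7 requires recording without limit by source. Staff who follow the former may not record events known only from a parent, a facilitator's observation, MRI staff or a treating clinician, including SAEs that a participant cannot report.

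Any loss would favour the under-15% criterion and make the Section 9.4 review less likely. The documents give neither an event rate nor a capture rate, so its size is unknown; it could be nil if staff follow Section 7 in practice. The conclusion rests on the current protocol text and assumes that the unseen forms and monitoring plan do not already resolve the conflict. It should be corrected, because safety ascertainment should not depend on which section a staff member follows.

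**What to change.** 1. In Section 6.2.1, replace the sentence with: *AE and SAE forms are completed whenever an event becomes known to the study team from any source (participant, parent or guardian, facilitator, MRI or study staff, treating clinician).*
2. Align the triggers in Sections 6.2.4, 6.2.5 and 10.1, so that a Yes on the CORS is one way to open the AE form and classification as serious opens the SAE form, as Section 7.2 already provides.
3. Reconcile the Section 6.2.5 statement on follow-up after stopping with the 7-day and 30-day window in Sections 7.4, 7.5 and 8.
4. Optionally, state that the inquiry at the next attended visit covers the whole period since the last attended visit, including missed sessions.

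The cost is a wording amendment, a few more forms and possibly a slightly higher recorded AE rate. No new visit or staff is needed.

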6.2.2 Enrollment, Baseline, and/or Randomization

Enrollment

The current study will utilize a single informed signed consent form that describes both screening and study procedures. Thus, in the current study, the enrollment date is defined as the date all of the screening criteria are met and the individual agrees to participate which is also the same date as the randomization date (i.e., Visit 1 [Day 0]). Please see above, Section 6.1, Schedule of Evaluations Table. The enrollment date will be recorded on a case report form (please see included Randomization and Enrollment form) along with the allowable window between screening and randomization (please see above section, "Screening", for the precise allowable time window between screening and randomization).

Baseline Assessments

The following baseline evaluations will occur on Visit 1 (Day 0) of the study:

MRI brain scan. An MRI brain scan will be acquired at baseline to compare

- against the final MRI brain scan that will be obtained at the final visit (Visit 14).
- Strengths and Difficulties Questionnaire (SDQ). Emotional problems will be assessed in all participants at baseline using the SDQ in order to compare with the SDQ that will be collected at the final visit (Visit 14).

Randomization

Computer-generated randomization will precede intervention administration in the current randomization study. The time window for randomization relative to completion of screening and baseline will be 24 hours (i.e., randomization as well as completion of screening and baseline will all occur the same day). The time window for initiation of study intervention relative to randomization will be 4 (four) weeks.

6.2.3 Blinding

There will be one unblinded research assistant (RA) who will be responsible for: (1) scheduling and helping set-up the delivery of the TARA intervention, and (2) providing unblinded case-by-case reports to the study Independent Monitors (IM); this RA will have no access to data and no involvement in data monitoring and analyses.

Since the Study subjects and TARA Instructors/Practitioners can not be blinded to the Intervention group assignment (please see below, Table 1 Blinding Table), there will not be an individual authorized to break the blind, circumstances for breaking the blind, or procedures for breaking the blind. Which stake holders will be blinded, what the stake holders will be blinded to, and the procedures for retaining the blind for the different stake holders for the intervention group assignment, primary mechanistic outcome measure, and clinical/functional outcome measure are described below in Table 1 (please see below, Table 1. Blinding Table).

Table 1. BLINDING TABLE

Stake holder	Intervention group assignment	Primary Mechanistic Outcome Measure	Clinical/ Functional Outcome Measure
Study subjects/Patients	Not blinded	Blinded	Blinded
casjooton anome	The study subjects/patients will know which intervention group they have been assigned to. Thus, by necessity, they will be only unblinded to the intervention group assignment.	The study subjects/patients will be blinded to the Primary Mechanistic Outcome Measure for the entire duration of the project.	The study subjects/patients will be blinded to the Clinical/Functional Outcome Measure for the entire duration of the project.
Instructors/ Practitioners	Not blinded	Blinded	Blinded
	The TARA Instructors/Practitioners must— by necessity—be only unblinded to the intervention group assignment in order to deliver the	All of the TARA Instructors/ Practitioners will be blinded to the Primary Mechanistic Outcome	All of the TARA Instructors/Practitioners will be blinded to the Clinical/Functional Outcome

	TARA intervention to the participants.	Measure for the entire duration of the study.	Measure for the entire duration of the study.
Outcome Assessors	Blinded All of the Outcome Assessors will be blinded to group assignment until after the database is locked. In order to blind the Outcome Assessors, each adolescent subject will be assigned a unique numerical identifier to mask the identity of the subject and also mask any private information that is linked to the subject. Coding and assignment of the unique numerical identifier will occur at the time of subject consent. This unique numerical identifier will be attached to all data acquired from adolescent subjects. Participants will be instructed not to discuss with any of the research study staff which group they have been assigned to during the entire duration of the study.	Blinded Neuroimaging Outcome Assessors will be blinded to clinical outcome assessments. Similarly, Clinical Outcome Assessors will be blinded to the neuroimaging outcome assessments. The clinical Outcome Assessors and neuroimaging Outcome Assessors will be separate study staff who will work in separate offices located on separate campuses at UCSF. The clinical Outcome Assessors and neuroimaging Outcome Assessors will not communicate with one another regarding the outcome of their separate assessments at any time point during the course of the study until after the database is locked. Blinded	Clinical Outcome Assessors will be blinded to the neuroimaging outcome assessments. Similarly, neuroimaging Outcome Assessors will be blinded to clinical outcome assessments. The clinical Outcome Assessors and neuroimaging Outcome Assessors will be separate study staff who will work in separate offices located on separate campuses at UCSF. The clinical Outcome Assessors will not communicate with one another regarding the outcome of their separate assessments at any time point during the course of the study until after the database is locked.
Statistician	The Data Analysts and Statistician will be blinded to the intervention group assignment until after the database is locked. The Data Analysts and Statistician will be unblinded after the database is locked at the time of the data analysis.	The Data Analysts and Statistician will be blinded to the Primary Mechanistic Outcome Measure until after the database is locked. The Data Analysts and Statistician will be unblinded after the database is locked at the time of the data analysis.	The Data Analysts and Statistician will be blinded to Clinical/Functional Outcome Measure until after the database is locked. The Data Analysts and Statistician will be unblinded after the database is locked at the time of the data analysis.
Principal Investigators	Blinded The Principal Investigators (PIs) will be blinded to the intervention group assignment during the entire course of the study until after the database is locked. Since the safety of all of the participants is of paramount importance, there is a risk of	Blinded The PIs will be blinded to the Primary Mechanistic Outcome Measure during the entire course of the study until after the database is locked.	Blinded The PIs will be blinded to the Clinical/ Functional Outcome Measure during the entire course of the study until after the database is locked.

inadvertently unblinding of the co-Pl, [name], if a safety concern arises (e.g., suicidal ideation in a participant). However, even if [name] is inadvertently unblinded in order to ensure the safety of the subject, [name] and [name] will both remain blinded to both the Primary Mechanistic Outcome Measure and Clinical/Functional Outcome Measure for the entire duration of
to ensure the safety of the subject, [name] and [name] will both remain blinded to both the Primary
and Clinical/Functional Outcome

